For studies that interview women and/or men ages 15–17 years, consent will be obtained from an adult in the household to conduct the interviews or, in the case of emancipated minors (according to local legal definition), they will give their own consent.

Households within each sampled cluster will be visited by the data collectors. Interviewers will ask to speak to an adult (18 years of age or whatever the local legal age of majority is), and if available the interviewers will ask screening questions (and fill out a screening form) to determine whether an eligible mother or father is present in the household. The screening form will be destroyed at the end of the fieldwork. If the answer is yes, and he or she is home and he or she agrees to participate following an informed consent/assent process, then he or she is interviewed. If he or she is not home but expected back within 30 minutes, the interview team will return to the house no more than three times before finishing all the interviews in the area. If unavailable, he or she will be counted as "Non-response" and substituted with someone from another household.

When no eligible mother or father is available in a household, then the interview team proceeds to the next house selected to be visited. If a mother has more than one child age 0–59 months, normally they will be asked about the youngest child. However, for some countries, it can be predetermined to select one of the mother's children at random.

Sample Size Determination

Specific sample sizes will vary from country to country. However, sample sizes will be calculated to provide estimates with confidence levels of 95 percent and precision of 10 percent for key indicators. For stratified random sampling and LQAS the design effect is 1. For 30-cluster sampling a design effect of 2 will be assumed. For all cases, if indicators are to be disaggregated, the total sample size must be multiplied by the number of disaggregation categories; if parallel sampling is needed the sample size must be increased to ensure adequate sample sizes for all indicators collected. Final sample sizes will be powered on the most important indicators, which may result in wider confidence intervals for a few of the other indicators.

For individual studies, decisions will be made regarding the most important indicators for which to collect information. The sample size will be powered for these indicators. After this the study will use the

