- 3. Each individual respondent will be asked to spend about 60–75 minutes with the interview team, including introductions, description of privacy measures, consenting, and responding to interview questions. Respondents will *not* be followed up for additional information. The majority of the studies will be cross-sectional of 1–4 months' duration per each data collection period.
- 4. The interview team will provide a brief data analysis plan and a description of variables to be derived. Each survey module contains indicator definitions and tabulation plans. Analysis will generally focus on generating frequencies and occasionally on cross-tabulations. (See modules for details.) For example, the on the data tabulation plans for selected key maternal indicators is based on data collected through the Maternal and Newborn Care Module. Any statistical software or hand tabulation procedure may be used as long as standardized tabulation plans are followed. In addition, for LQAS, decision rule tables will be used to assess whether or not a supervision area has reached expected results. However, care will be taken not to prematurely remove resources from any supervision area

Illustrative Key Maternal Health Indicators		
Indicator 1.2	Antenatal Care (4+ visits)	
Indicator 1.13	IPT _P (3+)	
Indicator 1.14	LLIN Use	
Indicator 2.1	Skilled Attendant at Birth	
Indicator 2.2	Facility Birth	

The following are examples of indicators and tabulation plans from the MNC module.

Data Tabulation Plans ¹⁰			
I.2, 6.2 Antenatal Care (4+) Percentage of mothers of children ages 0– 23 months who had four or more antenatal visits while pregnant with their youngest child	Number of mothers of children ages 0–23 months who had four or more antenatal visits while pregnant with their youngest child 4 ≤ MN105 < 98		
	Total number of mothers of children ages 0–23 months in the survey	× 100	

¹⁰These tabulation plans and indicators are examples from one of the current modules (Maternal and Newborn care). Target populations (denominators) for these indicators may vary, depending on the specific survey. Variations will be explained in amendments submitted for specific surveys.

Data Tabulation Plans ¹⁰			

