3.Intermittent Preventive reatment for Pregnant Women of alaria (3 doses) rcentage of mothers of children age 0– months who received three or more	Number of mothers of children age 0–23 months who received three or more doses of Intermittent Preventive Treatment (IPTp) for malaria while pregnant with their youngest child MN127 ≥ 3		
doses of Intermittent Preventive Treatment for pregnant women (IPTp) for malaria while pregnant with their youngest child	Total number of mothers of children age 0–23 months in the survey	× 100	
 1.14 Long-Lasting Insecticidal Net (LLIN) Use Percentage of mothers of children ages 0– 23 months who slept under an LLIN all of the time or most of the time while 	Number of mothers of children ages 0–23 months who slept under an LLIN all of the time or most of the time while pregnant with their youngest child [(MN129 = 1 OR 2) AND (MN130 = 1 OR 2)]		
pregnant with their youngest child	Total number of mothers of children ages 0–23 months in the survey	× 100	
2.2, 7.2 Facility Birth	Number of last-born children ages 0–23 months who were born in a health facility (excludes mobile		
Percentage of last-born children ages 0–23 months who were born in a health facility	clinic)		
	MN201 = Any response [A–C, F, G]	w 100	
	Total number of children ages 0–23 months in the survey	X IUU	

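### The IPTp 3+ numerator lacks the upper bound that the same table gives ANC 4+, so any numeric special code of 3 or more on MN127 would count as three doses received

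*Protocol*

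**What the plan says.** Protocol section 4, Study Implementation item 4, lists IPTp 3+ among the illustrative key maternal health indicators and then gives tabulation plans from the Maternal and Newborn Care module.

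- **IPTp 3+.** The numerator's code line is "for malaria while pregnant with their youngest child MN127 ≥ 3". The denominator is "Total number of mothers of children age 0–23 months in the survey".
- **ANC 4+.** The numerator's code line is 4 ≤ MN105 < 98. The denominator is likewise all mothers of children in that age range in the survey.

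The same item makes such plans the rule to follow: "Any statistical software or hand tabulation procedure may be used as long as standardized tabulation plans are followed". Footnote 10 labels the plans as examples from one module and says that denominators may vary by survey. It does not say that numerator rules may vary.

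On precision, Sample Size Determination says that "sample sizes will be calculated to provide estimates with confidence levels of 95 percent and precision of 10 percent for key indicators".

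**The concern.** Both items score a number of times against a minimum. One is closed at the top and the other is open, and no reason is given. Nobody has 98 antenatal visits in a pregnancy, so the sensible reading of the bound on MN105 is that 98 and above are special codes, for example for an unknown number, which must not count as success. If MN127 follows the same convention, a mother who could not give a number of doses passes the test of being at least 3.

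Any such error can only raise coverage, and a larger sample does not reduce it. Because the protocol is generic and meant for many country surveys, one loose line can be repeated. Two uses of the indicator would be exposed: classification of supervision areas by lot quality assurance sampling (LQAS) decision rules, and comparison between rounds when the share of special codes differs between them.

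**Working it through.** There is no stated figure for this rule to reproduce. The check applies the two rules to possible codes and then works out the gap between them.

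**1. Which codes pass**

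| MN127 value | Printed rule (≥ 3) | Bounded rule (3 ≤ MN127 < 98) |
|---|---|---|
| 0, 1, 2 | no | no |
| 3, 4 | yes | yes |
| 8 | yes | yes |
| 97 | yes | yes |
| 98, 99 | yes | no |

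The rules differ only at 98 and above. If the special code were 8, the bound at 98 would not remove it.

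**2. Gap between the two rules**

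The denominator keeps every mother under both rules. Therefore:

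gap in coverage = (mothers coded 98 or above) / (all mothers in the denominator)

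The inputs are n = 96 and n = 192, the protocol's single-survey sample sizes (1.96² × 0.25 / 0.10² = 96.04, stated as 96; doubled for the 30-cluster design, 192). The following are assumptions and are not in the documents: coverage near 30% under the bounded rule (29/96 or 58/192, both 30.2%) and the special-code shares.

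| Assumed share | n = 96: bounded → printed | n = 192: bounded → printed |
|---|---|---|
| 0% | 30.2% → 30.2% | 30.2% → 30.2% |
| 2% | 30.2% → 32.3% | 30.2% → 32.3% |
| 5% | 30.2% → 35.4% | 30.2% → 35.4% |
| 10% | 30.2% → 40.6% | 30.2% → 40.1% |

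Small departures from whole points come from rounding to whole mothers (for example, 5/96 = 5.2 points). At an assumed 10% share the gap is about as large as the planned precision of 10 points.

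**3. Bias against true coverage**

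Some mothers with a special code will in fact have had three or more doses. Therefore:

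bias of the printed rule = P(special code) × P(fewer than 3 doses, given special code)

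This is at most P(special code). For illustration, take true coverage of 20% in all mothers, with or without a special code:

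- 5% share: 0.95 × 0.20 + 0.05 = 0.24, a bias of 4 points.
- 10% share: 0.90 × 0.20 + 0.10 = 0.28, a bias of 8 points.

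One point per 1% of mothers is thus the exact gap between the two rules, and only a ceiling on the bias against the truth.

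**4. Small samples**

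With the LQAS minimum of 19 interviews per supervision area, one such answer moves the area's figure by 1/19 = 5.3 points.

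**The case against.** The strongest reply is that the decisive fact is absent. The protocol does not show the MN127 question, its response codes or its skip pattern, and nowhere says what 98 means, even for MN105. If an unknown number is left blank or stored as text, the printed rule does no harm. This stands, and it is why the point is conditional.

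It can also be said that the wording beside the code line correctly asks for mothers who received at least three doses, and that the table is illustrative and refers the reader to the modules. Both are true, but neither cures the line. The code line is what gets executed, it is looser than the wording beside it, and the protocol requires standardized plans to be followed. The examples label lowers the weight of the point without removing it.

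A reader might infer three stronger things that the documents do not support:

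- **That coverage is inflated.** This needs a numeric special code of 3 or more on MN127, which is inferred only by analogy with MN105.
- **That mothers who took no treatment and were skipped past MN127 would also be counted.** This needs a skip pattern that is not shown and software that ranks missing values above all numbers. The protocol fixes no software and allows hand tabulation.
- **That change between rounds would track unknown answers instead of coverage.** It would reflect both, and a stable share of special codes would largely cancel.

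**Conclusion.** The point holds in conditional form. It is certain that the IPTp 3+ rule has no upper bound while the ANC 4+ rule in the same table has one. It is not established that MN127 contains a code that the open rule would let in.

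If it does, reported coverage exceeds the bounded figure by exactly the share of mothers so coded, and exceeds true coverage by no more than that share. The documents give no such share. The 2%, 5% and 10% used here are assumptions, and zero is possible. A reader might take the 10-point case as the expected harm to the planned precision, but it is only the top of an assumed range.

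This is a low-cost consistency correction to a listed key indicator. It is not a demonstrated bias.

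**What to change.** 1. Look up MN127's response codes in the Maternal and Newborn Care module.
2. If 98 is a special code, print the numerator as 3 ≤ MN127 < 98. If another value is used, exclude that value explicitly, since a bound at 98 would not catch a lower one.
3. Keep all mothers in the denominator, as ANC 4+ does.
4. State that a blank or skipped MN127 does not satisfy the numerator condition. This governs the comparison only. Do not recode all missing values as treatment not received, because that would merge proper skips with item non-response.
5. Check the module's other count items for the same omission.

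The cost is a codebook check and one or two lines in the tabulation plan. Sample size, fieldwork and the questionnaire are unaffected.
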